9 STATISTICAL ANALYSES

9.1 General Considerations

Continuous measures will be summarized with sample size, mean, median, standard deviation, minimum and maximum; categorical measures will be presented with the counts and percentages of subjects in each category.

10 STUDY ENDPOINTS

10.1 Safety Endpoint

An adverse event (AE) is any undesirable clinical or medical occurrence associated with the use of the device, procedure, or participation in the study, which does not result in serious injury or illness related to the surgical procedure or the device.

Adverse events will be counted regardless of severity, seriousness, onset, duration, or relation to study treatment.

A serious adverse event (SAE) is any untoward medical occurrence that

- results in death
- is life-threatening
- requires inpatient hospitalization or prolongation of existing hospitalization
- results in persistent or significant disability/incapacity
- requires medical or surgical intervention to prevent life-threatening illness or injury or permanent impairment to a body structure or a body function
- leads to fetal distress, death, or congenital abnormality or birth defect
- is a medically important event or reaction

For any SAE, if the Primary Investigator judges that there is a logical connection (caused or contributed to) between the use of the device and the occurrence, the SAE will be noted as device-related.

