## **STUDY OBJECTIVES**

### **Primary Objectives**

The primary objective of this multi-site study is to investigate the safety and efficacy of programming cochlear implants through telecommunication.

Safety will be determined by characterizing the safety profile of device and/or procedure related adverse events associated with facilitated remote MAP programming, unassisted MAP programming and audiologist live MAP programming. An adverse event (AE) is the development of an untoward medical occurrence or the deterioration of a pre-existing medical condition following or during exposure to an investigational product, whether or not considered causally related to the product.

Efficacy will be determined by showing that performance on the CNC word recognition test using a remotely programmed MAP is no worse than when using a live programmed MAP.

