### ADVERSE DEVICE EFFECTS

To monitor subject safety throughout this IDE study, any procedure or device related adverse events will be recorded. Information on all adverse events will be maintained by event type. The investigator will complete an Adverse Event form if any adverse event is reported or observed for a subject during this IDE, even if they were acknowledged as risk factors in the Informed Consent form.

Adverse device effects refer to any undesirable clinical or medical occurrence associated with use of the device or participation in the study. Any/all adverse device effects are to be recorded via the Adverse Event form. Adverse device effects will be reported if observed, even if they were acknowledged as risk factors in the Informed Consent form.

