5 ABBREVIATIONS AND DEFINITIONS

Abbreviation / Term	Definition
ADE	Adverse Device Effect - any untoward and unintended response to an investigational medical device
AE	Adverse Event - any untoward medical occurrence in a subject
CI	Cochlear Implant
CRF	Case Report Form
eCRF	Electronic Case Report Form
Enrolled	A subject is enrolled when he/she meets all inclusion/exclusion criteria and signs the informed consent form
Facilitator	A trained staff member at the programming site
IDE	Investigation Device Exemption
Live Programming	Traditional face to face programming interaction between a recipient and an audiologist at the same physical location
MAP	A program that defines the individualized parameters of recipients for a specific speech coding strategy
Remote Programming	A programming interaction between a recipient and an audiologist that occurs via telecommunication technology when the two parties are at different physical locations
SAE	Serious Adverse Event – an adverse event that: 
• Led to death• Led to a serious deterioration in the health of the subject, that

	
either resulted in a life-threatening illness or injury, or a permanent impairment of a body structure or a body function, or in-patient hospitalization or prolongation of existing hospitalization, or resulted in medical or surgical intervention to prevent life-threatening illness or injury or permanent impairment to a body structure or a body function
 
 • Led to fetal distress, fetal death or a congenital abnormality or birth defect
SAP	Statistical Analysis Plan

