10.1.1 Safety Endpoint

The objective of the safety analysis is to characterize the safety profile of device and/or procedure related adverse events associated with facilitated remote MAP programming, unassisted MAP programming and audiologist live MAP programming.

All Adverse Events will be tabulated according to the study interval, the number of procedure-related events, and the number of device-related events. Procedure- and device-related adverse events will be summarized as rates, where the numerator for each rate will be the number of subjects with at least one procedure- or device-related event, and the denominator will be the total number of subjects.

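### The adverse-event definition in SAP 10.1 conflicts with the rest of the plan and, read literally, drops serious device-related events from the safety outputs

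*SAP*

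**What the plan says.** SAP 10.1 (Safety Endpoint) defines an AE as an undesirable occurrence linked to the device, the procedure or taking part in the study, "which does not result in serious injury or illness related to the surgical procedure or the device". The next sentence reads: "Adverse events will be counted regardless of severity, seriousness, onset, duration, or relation to study treatment". The section then lists SAE criteria. Its only rule for handling SAEs is that, where the investigator sees a logical connection with use of the device, "the SAE will be noted as device-related".

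SAP 5 (Abbreviations and Definitions) defines an AE as "any untoward medical occurrence in a subject" and an SAE as "an adverse event that" meets one of its listed criteria.

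The Protocol, under Primary Objectives, says that an AE "is the development of an untoward medical occurrence or the deterioration of a pre-existing medical condition", whether or not it is causally attributed to the product. Under Adverse Device Effects it says that "any procedure or device related adverse events will be recorded".

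The planned output is in SAP 10.1.1: "All Adverse Events will be tabulated according to the study interval, the number of procedure-related events, and the number of device-related events". Procedure-related and device-related AEs are then each given as a rate, namely subjects with at least one such event divided by all subjects.

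**The concern.** The analysis section and the definitions section of the same SAP give different meanings to the term on which the safety tables are built. SAP 10.1.1 tabulates AEs, and SAP 10.1 is the nearest definition of an AE. Taken at its word, that definition removes one group of events, those with a serious consequence related to the device. These are the events a reader of a safety summary most needs to see.

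The primary safety endpoint is descriptive, so the counts and rates are the whole result and no test elsewhere would expose an omission. Nor is there a second output to catch it: neither SAP 10.1.1 nor SAP 12 to 14 plans an SAE table, rate or listing. The SAP does not say which of its conflicting sentences prevails.

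**Working it through.** The plan states no safety figure that could be reproduced, so the check is mainly a comparison of texts, followed by a small illustration.

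**Is a serious event an AE?**

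| Place | Answer |
|---|---|
| SAP 10.1, definition | No, if the serious injury or illness is related to the surgical procedure or the device |
| SAP 10.1, next sentence | Yes; seriousness and relation do not matter for counting |
| SAP 5 | Yes; an SAE is one kind of AE |
| Protocol, Primary Objectives | Yes; no seriousness exclusion, and causality is irrelevant |

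Three of the four favour inclusion. The one that does not is the definition that comes directly before the safety outputs.

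**What does the clause reach?** It names the surgical procedure and the device. The study procedures in the Protocol are programming sessions, speech testing and questionnaires; no surgery is described. A serious event related only to the programming procedure is therefore outside the clause and remains an AE. A serious event related to the device is inside it, including one that is also related to programming.

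**What happens in SAP 10.1.1 if the clause is applied?** A serious device-related event leaves the AE tabulation by study interval and the count of device-related events. If it is the subject's only device-related event, the subject also leaves the numerator of the device-related rate but stays in the denominator. If the subject has another device-related event that is not serious, the subject rate is unchanged and the event count is one too low.

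**Size, as an illustration only.** The documents give no expected event rate, so assume one subject whose only device-related event is serious, and no other subject with a device-related event. N = 40 is the maximum enrolment in SAP 7. N = 26 is the minimum evaluable number in SAP 8 and shows the range. The exact (Clopper-Pearson) 95% limits for x of N are:

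- lower = Beta quantile(0.025; x, N − x + 1), set to 0 when x = 0
- upper = Beta quantile(0.975; x + 1, N − x), which for x = 0 equals 1 − 0.025^(1/N)

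| N | Clause applied | Event counted | Change |
|---|---|---|---|
| 40 | 0/40 = 0% (0 to 8.8%) | 1/40 = 2.5% (0.1 to 13.2%) | 100/40 = 2.5 points |
| 26 | 0/26 = 0% (0 to 13.2%) | 1/26 = 3.8% (0.1 to 19.6%) | 100/26 = 3.8 points |

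The SAP itself plans no confidence intervals for these rates; they are added here to show the scale.

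**The case against.** The strongest reply is that the surrounding text already settles the matter. The only sentence that governs counting says seriousness is irrelevant, and it would do little work if serious events were not AEs. SAP 5 and the Protocol agree with it. SAP 10.1 also marks qualifying SAEs as device-related, and SAP 10.1.1 counts device-related events, so the natural reading is that the marked SAEs feed that count. This stands, and it makes the effect conditional. It does not remove the conflict. The counting sentence applies to AEs just after that class has been narrowed, and SAP 10.1, unlike SAP 5, does not describe SAEs as a kind of AE. A programmer working from SAP 10.1 alone could defend either choice.

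A reader might go further and infer that the sponsor plans to leave serious events out. The documents do not support that. The Protocol requires related events to be recorded under Adverse Device Effects, and unanticipated serious device effects to be reported under the section that follows. The gap is in the analysis rule, not in data collection or regulatory reporting.

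A reader might also infer that every serious related event is excluded. That is too broad, because serious events related only to programming fall outside the clause.

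It is also fair to say that 0/40 against 1/40 would look the same in any study of 40 subjects. The figures show scale and are not evidence that such events will occur.

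**Conclusion.** The contradiction is real and lies in the current SAP text. It is a wrong definition stated for the primary safety endpoint, not a missing detail, and it should be corrected. Its effect is conditional: only if the clause is applied literally do serious device-related events drop out of the SAP 10.1.1 counts and the device-related rate, with no planned SAE output to reveal them.

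Under the illustrative assumption, the size is 2.5 percentage points per affected subject at N = 40. In practical terms, it separates a table with no device-related event from one that contains a serious event. The safety endpoint has no hypothesis or threshold, and study success in SAP 11 rests on word recognition alone, so no success decision changes.

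The conclusion assumes that serious injury or illness in the clause covers the same kind of event as the SAE criteria, and that no output beyond those described in the SAP is planned.

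**What to change.** 1. In SAP 10.1, delete the clause that excludes serious injury or illness, and use the SAP 5 definition of an AE, under which SAEs are a subset.
2. In SAP 10.1.1, state that SAEs are included in the procedure-related and device-related counts and rates.
3. Add SAE counts to the SAP 10.1.1 table, by study interval and relatedness. This is useful under either reading, since SAEs that are counted could not otherwise be told apart from minor events.

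Two items are housekeeping only. Extend the SAE relatedness sentence in SAP 10.1 to the procedure as well as the device, since SAP 10.1.1 reports both. Use one SAE list in SAP 5 and SAP 10.1; at present SAP 10.1 includes medically important events and SAP 5 does not.

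The cost is SAP wording and a few table rows. No new visits, data or denominators are needed.

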10.1.1 Safety Endpoint

The objective of the safety analysis is to characterize the safety profile of device and/or procedure related adverse events associated with facilitated remote MAP programming, unassisted MAP programming and audiologist live MAP programming.

All Adverse Events will be tabulated according to the study interval, the number of procedure-related events, and the number of device-related events. Procedure- and device-related adverse events will be summarized as rates, where the numerator for each rate will be the number of subjects with at least one procedure- or device-related event, and the denominator will be the total number of subjects.

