## Investigational Procedures

### Design Overview

Cochlear implant recipients aged greater than 12 years of age will be asked to participate in this clinical study. A single-subject research design (in which each subject serves as his or her own control) is appropriate since it accommodates the heterogeneity that characterizes hearing-impaired populations. Subjects will be tested at three intervals: the first, third, and last of five total visits.

At **Visit One**, the subjects will be screened and consented by their primary audiologist. They will complete speech testing in the unilateral condition, using their current MAP which they must have been using for no more than 12 months. Subjects will schedule Visit 2 to fall within one month after Visit 1.

**Visit Two** will take place at a pre-determined site, different than the subject's primary programming center. The subjects will participate in a remote location programming session conducted by their primary audiologist via telecommunication, with on-site assistance provided by a trained facilitator. This MAP will be referred to as the Facilitated MAP.

Subjects will return home and use this new program for 2-4 weeks, after which time they will return to their primary programming center for Visit 3.

For **Visit Three** (2-4 weeks after Visit 2), subjects will return to their primary programming center for speech testing using their remotely programmed MAP (Facilitated MAP), and to complete a comparative survey.

**Visit Four** will occur 2-4 weeks after Visit 3 at the same pre-determined site as Visit 2. The subjects will participate in a second remote programming session conducted by their primary audiologist via telecommunication, but the subject will serve as his or her own facilitator. This MAP will be referred to as the Self MAP.

Subjects will return home and use this new program for 2-4 weeks, after which time they will return to their primary programming center for Visit 5.

At **Visit Five**, subjects will complete speech testing using their second remotely programmed MAP (Self MAP). Subjects will also complete a comparative survey and a questionnaire regarding their experience with remote programming.

The following study procedures will be completed:

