**Figure 2: Study visit flow chart**

## Endpoint Testing

**Primary Safety Endpoint: Characterize the safety profile of device and/or procedure related adverse events associated with facilitated remote MAP programming, unassisted MAP programming and audiologist live MAP programming**

Safety Endpoint testing will occur at Visit 2 and Visit 4.

- Recipients will be MAPped via telecommunication by a remotely located audiologist.
- Any adverse events associated with the MAPping will be recorded on the New Adverse Event Reporting Form. Any AEs identified at Visit 2 or Visit 4 will be re-evaluated at subsequent visits and updated on the Follow Up Adverse Event Reporting Form.

**Co-Primary Efficacy Endpoint 1: Demonstrate that performance on CNC words using a remotely programmed facilitated MAP is no worse than when using a live programmed MAP**

Efficacy Endpoint 1 testing will occur at Visit 1 and Visit 3.

- **Visit 1:** Speech perception scores will be obtained in Program 1 (familiar/Live)
- **Visit 3:** Speech perception scores will be obtained in Program 2 (Facilitated MAP)

**Co-Primary Efficacy Endpoint 2: Demonstrate that performance on CNC words using an unassisted remotely programmed MAP is no worse than when using a live programmed MAP**

Efficacy Endpoint 2 testing will occur at Visit 1 and Visit 5.

- **Visit 1:** Speech perception scores will be obtained in Program 1 (familiar/Live)
- **Visit 5:** Speech perception scores will be obtained in Program 2 (Self MAP)

**Secondary Efficacy Endpoint: Demonstrate non-inferiority of unassisted remote MAP programming compared to facilitated MAP programming via performance on CNC words.**

Efficacy Endpoint 2 testing will occur at Visit 3 and Visit 5.

- **Visit 3:** Speech perception scores will be obtained in Program 2 (Facilitated MAP)
- **Visit 5:** Speech perception scores will be obtained in Program 2 (Self MAP)

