8 SAMPLE SIZE

Based on the variability observed in earlier studies, it was determined using PASS (NCSS Statistical Software) that a minimum of 26 subjects would provide at least 90% power for hypothesis testing of the two co-primary endpoints at the 0.025 alpha level.

The planned sample size of 40 subjects will provide adequate power for hypothesis testing of the two co-primary endpoints at the 0.025 alpha level. The following general assumptions have been made:

- Paired T-tests of difference scores to test for non-inferiority with a non-inferiority margin of 10% for CNC word recognition
- One-sided 0.025 alpha level
- Assumed distribution for population (standard deviation)
- Desire for 90% power

The power analyses for the primary test metrics are provided below.

Sample size calculation for CNC word recognition:

Scenario (Non-inferiority)	Minimum Evaluable Sample Size Required
One-sided 0.025 alpha, 90% power, SD = 15%, NIM = 10% , true difference = 0	26

More subjects will provide additional power or a similar degree of power for more conservative assumptions. Because the non-inferiority sample size calculation assumes a true difference of 0 between remote and live MAP programming, we propose a sample size of 40 subjects to allow for:

1. the possibility that variability will be greater than expected,
2. the possibility that the true difference may be greater than 0, and
3. the possibility of subject attrition.

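### SAP 10.1.1 sets a safety objective by programming method but defines related-event rates only over all subjects, with no rate per method

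*SAP*

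**What the plan says.** SAP 10.1.1 aims to characterise the profile of device- and procedure-related events "associated with facilitated remote MAP programming, unassisted MAP programming and audiologist live MAP programming". The protocol makes this the primary safety endpoint (Study Summary; Endpoint Testing).

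SAP 10.1.1 then specifies two outputs:
- A tabulation: "All Adverse Events will be tabulated according to the study interval", and by the numbers of procedure-related and device-related events.
- Rates for related events, where "the denominator will be the total number of subjects". Above the line, affected people are counted rather than events: "the numerator for each rate will be the number of subjects with at least one procedure- or device-related event".

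The SAP defines no rate per interval or per method, and no rule that assigns an event to a method.

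Exposure is sequential. The facilitated session is Visit 2. The unassisted session is Visit 4, where "the subject will serve as his or her own facilitator" (Protocol, Design Overview). The protocol also states that "Safety Endpoint testing will occur at Visit 2 and Visit 4". Consent is taken at Visit 1, where nothing is programmed (Protocol, Methods, Visit 1). In SAP section 5, "A subject is enrolled when he/she meets all inclusion/exclusion criteria and signs the informed consent form", so enrolment does not depend on having had a session. SAP section 8 lists "the possibility of subject attrition" among its reasons for planning 40 subjects.

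**The concern.** The objective asks about each method, while the stated rates combine the methods. A reader who wants the proportion of subjects with a related event after unassisted programming will not find it defined anywhere. That is the session without on-site help, and the Protocol Introduction says the study will explore inconsistencies between the facilitator and recipient models of remote service.

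The denominator is a second difficulty. A subject who leaves before Visit 4 cannot have an event from unassisted programming, yet may still be counted in the total. By the visit windows, Visit 4 can fall about three months after consent (up to 1 month to Visit 2, up to 4 weeks to Visit 3, up to 4 weeks to Visit 4), so some loss before it is possible.

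With no hypothesis test on safety, the description is the whole result. If the rates do not match the question, the endpoint is left for the reader to assemble afterwards without a prespecified rule.

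**Working it through.** **Inputs.** Planned N = 40 and minimum evaluable n = 26 (SAP section 8). The documents give neither an attrition rate nor an expected event rate, so both are assumed below and shown as ranges. Let r be the number of subjects who have the Visit 4 session, taken from 26 to 40.

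**The plan's own figure.** A one-sample t-test for non-inferiority with margin 10, SD 15, true difference 0 and one-sided alpha 0.025 has power 0.892 at n = 25 and 0.904 at n = 26 (noncentral t). The stated 26 is therefore reproduced. It is a power requirement for CNC words, not a retention forecast, and serves here only as a lower bound for r.

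**Case A: unassisted-session events over all subjects.** If x subjects have such an event, the reported rate is x/N and the rate among those exposed is x/r. Reported/exposed = (x/N)/(x/r) = r/N.

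| r of 40 | factor r/40 | 2 affected: over 40 | 2 affected: over r | exact 95% upper limit over r |
|---|---|---|---|---|
| 40 | 1.00 | 5.0% | 5.0% | 16.9% |
| 36 | 0.90 | 5.0% | 5.6% | 18.7% |
| 32 | 0.80 | 5.0% | 6.25% | 20.8% |
| 26 | 0.65 | 5.0% | 7.7% | 25.1% |

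With no affected subjects, the upper limit of the exact two-sided 95% interval is 1 − 0.025^(1/n). That is 8.8% for n = 40, 9.7% for 36, 10.9% for 32 and 13.2% for 26.

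**Case B: one rate combining both sessions.** Let pf and ps be the risks at the facilitated and unassisted sessions, and q = r/40. Assume that all 40 have the facilitated session and that events at the two sessions are independent. The expected combined rate is

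pf(1 − q) + q[1 − (1 − pf)(1 − ps)] = pf + q·ps·(1 − pf).

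- pf = ps = 5%, r = 40: 0.05 + 1.00 × 0.05 × 0.95 = 9.75%, above the unassisted 5%.
- pf = ps = 5%, r = 26: 0.05 + 0.65 × 0.05 × 0.95 = 8.1%, still above 5%.
- pf = 2%, ps = 10%, r = 40: 0.02 + 1.00 × 0.10 × 0.98 = 11.8%, above 10%.
- pf = 2%, ps = 10%, r = 32: 0.02 + 0.80 × 0.10 × 0.98 = 9.8%, just below 10%.
- pf = 2%, ps = 10%, r = 26: 0.02 + 0.65 × 0.10 × 0.98 = 8.4%, below 10%.

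With full follow-up the combined rate cannot fall below the unassisted risk, because it counts every subject with an unassisted-session event. With dropout it can lie on either side.

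**The live method.** Visit 1 only tests the existing MAP. The regular programming session lies 1 to 12 months before Visit 1 (Protocol, Study Summary), and Visits 2 and 4 are remote. No choice of denominator yields a rate for a live session within the study.

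**The case against.** A reader might infer that the stated rule makes unassisted programming look safer than it is. The documents do not support that as a general claim. Case B shows that a combined rate often exceeds the risk of a single session. Understatement is certain only in Case A, when unassisted-session events are put over all subjects and some of them missed Visit 4.

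A reader might also infer a single pooled rate for all related events. SAP 10.1.1 speaks of rates in the plural, most plausibly one procedure-related and one device-related. Both would still combine the programming methods.

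Other points against the concern have weight:
- Event counts by study interval, with subjects per visit and early withdrawals from SAP 12.1, allow a partial reconstruction, because interval approximates method in this sequential design. It is only partial: the tabulation covers all events, not subjects with a related event, and no rule links an event to a method.
- The total is not defined as all consented subjects. SAP 12.2 refers explicitly to enrolled subjects for demographics, and 10.1.1 does not use that term. The denominator is therefore unspecified, and it may or may not take in subjects who had no session.
- The margin from 26 to 40 also covers greater variability and a non-zero true difference, so reading all of it as dropout would be wrong.
- The endpoint is descriptive. Study success in SAP section 11 rests on CNC words alone.

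**Conclusion.** The point stands as a gap between objective and analysis. SAP 10.1.1 names three methods and defines no rate for any of them, and its denominator is not limited to subjects who had the session in question. A combined rate may lie above or below the risk of one method.

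The size of any understatement of the unassisted rate is conditional. It is the factor r/40 in Case A, from 1.00 with no dropout to 0.65 if only 26 of 40 reach Visit 4. The lower end is an assumption for illustration. At 36 of 40, two affected subjects move only from 5.0% to 5.6%.

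The consequence is modest, since no test or success criterion uses these rates. The change is still worth making because it is cheap and lets the primary safety endpoint answer its own question.

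**What to change.** Amend SAP 10.1.1 as follows.

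1. For each remote method, report the proportion of subjects with a procedure-related event and, separately, the proportion with a device-related event.
   - Facilitated: denominator, subjects who had the Visit 2 session; interval, from that session up to the Visit 4 session (or to withdrawal, if earlier).
   - Unassisted: denominator, subjects who had the Visit 4 session; interval, from that session to study end.
2. Give an exact 95% interval for each proportion.
3. Keep the overall rate as a supplement, and state which subjects make up the total.
4. Add an attribution rule. The familiar live MAP stays in slot #1 throughout (Protocol, MAP Programming Methods), so the interval alone does not settle which MAP an event belongs to.
5. State that the study contains no live programming session, so no comparable live-session rate can be given. Events between Visit 1 and Visit 2 can only be described as occurring on the familiar MAP.

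The cost is SAP wording, a few table rows and wider intervals per method. No visit or assessment is added. If the adverse event form does not record which program was in use at onset, the attribution rule may need one extra item on it.
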